The aim of this study is to determine if the monocytes from people with periodontal disease behave differently from those taken from healthy individuals in a way that heightens the risk of atherosclerosis. We will test the hypothesis that reduced levels of IGFBP-6 and altered Wnt signalling contribute to altered monocyte/macrophage pro-atherosclerotic behaviour in patients with periodontitis. Consequently, modification of IGFBP-6 and/or Wnt signalling will retard atherosclerosis and IGFBP-6, and Wnt signalling proteins will act as suitable biomarkers of atherosclerosis disease progression.

Objectives and methods:

- 1. To determine the underlying mechanism of regulation in monocytes/macrophages from people with periodontal disease compared with healthy controls we will assess four key stages that are essential for the development of atherosclerosis, mainly:
 - a. *Monocyte adhesion to endothelial cells:* human monocytes will be isolated using standard techniques. They will be labelled with calcein-AM for 30 minutes, and then incubated with a monolayer of cultured human coronary artery endothelial cells purchased from Promocell.

After 30 minutes the number of adherent monocytes will be quantified by image analysis.

b. *Invasion/Migration assays*: isolated human monocytes will be differentiated into macrophages by culture with 20ng/ml M-CSF for 7 days. Macrophages will be cultured in

Matrigel-coated transwells with 50ng/ml MCP-1 as chemoattractant in the lower chamber. After 72 hours, the number of migrated macrophages will be quantified by image analysis as described previously

c. *Phenotype of macrophages*: macrophage phenotype will be assessed by quantification of M1 (iNOS, IL-6) and M2 (arginase, IL-10) markers by Western blotting and ELISAs.

d. Lipid content of macrophages: Monocyte/macrophages will be incubated with 10µg/ml ox-LDL for 24 hours. Lipid content will be quantified by oil red O staining.
Endocytosis will be quantified using zymosan bead. Changes in RNA will be assessed using qPCR.

The *in vitro* experiments have been designed to determine the effect of increasing or decreasing the level of IGFBP6 and Wnt signalling using various approaches outlined in Table I below.

Ехр	Group 1	Group 2	Group 3	Experimental Question
A	Control + siRNA control	Control + BP6 siRNA	Periodontitis + siRNA control	Does silencing BP6 in control cells mimic efforts observed in cells from periodontal patients?

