В	Control + IgG control	Control + BP6 Nab	Periodontitis + IgG control	Does neutralizing IGFBP6 in control cells mimic effects observed in cells from periodontal patients?
С	Control + vehicle	Periodontitis + vehicle	Periodontitis + BP6	Does addition of IGFBP6 to cells from periodontal patients mimic control cells?
D	Control + vehicle	Periodontitis + vehicle	Periodontitis + ETC-159	Does inhibition of Wnt secretion (using ETC-159) in cells from periodontal patients mimic control cells?
E	Control + vehicle	Periodontitis + vehicle	Periodontitis + iCRT	Does inhibition of Wnt/b-catenin signalling (using iCRT) in cells from periodontal patients mimic control cells?
F	Control + vehicle	Control + 400ng/ml Wnt3a	Periodontitis + vehicle	Does treatment of control cells with Wnt3a mimic cell from periodontal patients?

Table I: summary of the design of in vitro experiments

2. Assessing the potential use of IGFBP6 and Wnt proteins as suitable biomarkers

a) Peripheral blood and saliva will be collected from patients with periodontal disease both pre and post treatment and age and gender matched healthy controls. b) Saliva samples will be collected from people with severe periodontitis and age and gender matched controls.

The seven Wnt proteins and IGFBP6 identified by our previous proteomic analysis will be quantified in plasma, isolated monocytes and saliva, and the levels in patients and controls statistically compared. Standard laboratory techniques including western blot and specific enzyme-linked immunosorbent assays (Bio-Plex, Bio-Rad Laboratories Ltd. Hertfordshire, UK) will be used to assess for changes.

This will determine whether IGFBP6 and/or any of the seven Wnt pathway proteins are associated with periodontitis and could lead to future work investigating the role of these proteins in disease progression. Is it likely that other novel findings will be identified and scope to explore these will be undertaken under the current protocol.

See protocols 1-3.

Study sites

 University Hospitals Bristol and Weston NHS Foundation Trust ,[name]

Translational Health Sciences, Research Floor, Level 7, University of Bristol, Bristol Royal Infirmary, [name] (location of laboratory and storage location for samples)

Participants and recruitment

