Clinicians or a member of the dental team at the University of Bristol Dental School will approach participants who are attending the hospital for either periodontal assessment or regular dental appointments (healthy volunteers).

- Potential donors will be provided with the same participant information leaflet (see enclosed) containing information about the research. Sufficient time will be provided to participants prior to
- Written consent will be obtained from participants to allow for a basic periodontal examination, and collection of a blood sample. Every 5th person will be asked to provide a sample of saliva.

Inclusion/exclusion criteria for people with periodontitis

Inclusion:

- All people over the age of eighteen (18)
- Capacity to consent
- Attending a scheduled dental appointment at the University of Bristol Dental Hospital
- People with unstable severe periodontitis or a high susceptibility to periodontitis (as defined by the British Society of Periodontology 2019 implementation of the 2017 World Workshop Classification of periodontal and peri-implant diseases and conditions: Stage III/IV and Grade C.)
- At least 18 erupted teeth

Exclusion

- All people under the age of eighteen (18)
- Those who lack capacity to consent
- History of cardiovascular disease such as hypertension, angina, previous myocardial infarction, heart failure, aortic disease, arrhythmia, heart valve disease.
- History of autoimmune/autoinflammatory diseases such as Sjogren's syndrome,
 - rheumatoid arthritis, inflammatory bowel disease, systemic lupus erythematosus, or systemic sclerosis
- History of endocrine disease including diabetes mellitus types 1 and 2
- Currently taking antibiotics or has had antibiotics in the preceding 6 months
- People taking statins, non-steroidal anti-inflammatory medications, immunosuppressive medications or corticosteroids.
- Smokers of tobacco (including Vaping/e-cigarettes)
- History of salivary gland disease or oral mucosa disease

Inclusion/exclusion criteria for healthy volunteers

Inclusion:

- All people over the age of eighteen (18)
- Capacity to consent
- Attending a scheduled dental appointment
- People with no evidence of periodontitis
- At least 18 erupted teeth

Exclusion

- All people under the age of eighteen (18)
- Those who lack capacity to consent
- History of cardiovascular disease such as hypertension, angina, previous myocardial infarction, heart failure, aortic disease, arrhythmia, heart valve disease

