- History of autoimmune/autoinflammatory diseases such as Sjogren's syndrome,
 rheumatoid arthritis, inflammatory bowel disease, systemic lupus erythematosus, or
 systemic sclerosis
- History of endocrine disease including diabetes mellitus types 1 and 2
- Currently taking antibiotics or has had antibiotics in the preceding 6 months
- People taking statins, non-steroidal anti-inflammatory medications, immunosuppressive medications or corticosteroids.
- Smokers of tobacco (including Vaping/e-cigarettes)
- History of salivary gland disease or oral mucosa disease

Ethical Considerations and information

Blood and saliva samples will be collected from participants who are capable of informed decision making. Treating clinicians or an appropriately qualified member of their team will obtain informed consent from participants. In general terms, participants will be asked to provide a sample of blood and saliva that will be used in this study to better understand the link between periodontal disease and atherosclerosis. Participant information leaflets and consent forms will be provided (see enclosed).

Sample Collection

Objective 1 and 2b

Upon obtaining consent, the clinical practitioner will collect two tubes of peripheral blood (approximately 20mls in total) from the forearm of the person using standard venepuncture techniques.

The clinical practitioner will ask every 5th person to provide a saliva sample. Whole saliva will be collected in polypropylene vials using the passive drool method (2mls in total). The person will undergo a basic periodontal screen to assess gum health using the previously validated 'Basic Periodontal Exam' (BPE)/ 'Periodontal Probing Depth', as well as recording if there is 'bleeding on probing'. (Dietrich *et al.* 2019). The exam and collection of samples will occur before dental treatment begins. After blood and saliva has been collected, and the periodontal screen performed, the person will have no further participation in the study.

Objective 2a

Upon obtaining consent, the clinical practitioner will collect two tubes of peripheral blood (approximately 20mls in total) from the forearm of the person using standard venepuncture techniques, and saliva will be collected (2mls in total).

The person will undergo a basic periodontal screen to assess gum health using the previously validated 'Basic Periodontal Exam' (BPE)/ 'Periodontal Probing Depth' as well as recording if there is 'bleeding on probing'. (Dietrich *et al.* 2019)

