The person will then undertake their routine dental treatment. The time it takes for the successful completion of dental treatment varies, as do the number of necessary appointments, but typically it can take approximately 24 weeks. On completion of this dental treatment the person will be asked to provide one additional peripheral blood sample (approximately 20mls) and saliva (2mls in total) sample. After this second sample of blood and saliva has been collected these participants will have no further participation in the study.

For all the objectives listed above, the clinical practitioner will then anonymise all samples by allocating a code to the samples. Only the clinical practitioners will have access to the code that links the samples and people, not the researchers. Once anonymised, samples will be made available to the researchers, who will analyse the samples using established laboratory techniques as mentioned above.

Duration of participant involvement

Objectives 1 and 2b: participants will be actively involved in the study for approximately 20 minutes at their assessment appointment.

Objective 2a: from the time of their assessment appointment to the successful completion of their dental treatment, the participants will have taken part in the study for approximately 24 weeks. The total amount of time the participant will be actively involved in the study will be approximately 35 minutes, spread over the two appointments.

Sample size determination

From our previous data with similar experimental design and analyses, we have calculated the sample size (**power analysis**) using an online sample size calculator (https://clincalc.com/stats/samplesize.aspx) and p<0.005

Objective 1: Mechanism of regulation

Approximately 150 gum disease (severe periodontitis) participants and 150 control participants (good gum health) will be approached. From these approaches we hope to obtain samples of blood from 125 severe periodontitis and 125 control participants. The sample size is based on previously published studies and our own previous work, and shown to provide a 90% power to detect a 50% change. (Willi *et al.* 2014; Nanbara *et al.* 2012)

Objective 2: Biomarker potential

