a) Approximately 20 gum disease (severe periodontitis) participants and 20 control participants (good gum health) will be approached. From these approaches we hope to obtain samples of blood and saliva from 12 severe periodontitis and 12 control participant The sample size is required to provide >90% power to detect a 30% change in protein expression.

b) Approximately 30 gum disease (severe periodontitis) participants and 30 control participants (good gum health) will be approached. From these approaches we hope to obtain saliva samples from 20 people with severe periodontitis and 20 control participants
 The sample size is required to provide a 80% power to detect a 20% change. (Jasim *et al.* 2018)

Analysis

Data will be analysed by t-tests when two groups are compared or by ANOVA if more than two groups are assessed.

Withdrawal of participants

Participants will be informed that they can withdraw from the study at any stage- no reason needs to be provided. Withdrawal from the study will not affect their dental care.

Any blood and saliva donated by a participant is a gift, and any samples or data collected up until the point the participant wants to withdraw will be kept, used and included in analysis.

Safety and adverse events

There is minimum risk to taking blood from participants. All clinical study procedures will be carried out on clinics at Bristol Dental Hospital by appropriately trained staff. All cross infection controls will be implemented including those related to COVID 19. All study material is participant specific and all clinical study staff are trained in Good Clinical Practice (GCP). All procedures are performed by clinical staff that have appropriate qualifications and training.

A slight discomfort and bruising may be experienced due to withdrawal of blood. There should be no major adverse effects, pain, discomfort, distress, intrusion, inconvenience or changes to lifestyle as this is a routine blood donation of small volume. No adverse effects are associated with collecting saliva.

Any adverse events should be reported to [name] who will review, record and if necessary, report all events to the UHBW R&I office via the University Hospitals Bristol and Weston adverse event reporting system (UHBW undertake this role on behalf of the Sponsor).

Data management

Confidentiality:

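### Objective 1 (125 vs 125) states no age or gender matching and names only unadjusted tests, and the one-in-five saliva rule does not by itself deliver the matching promised for Objective 2b

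*Protocol*

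**What the plan says.** **Matching.** Matching appears only under Objective 2 of the Protocol's objectives and methods. For 2a, blood and saliva come from patients "both pre and post treatment and age and gender matched healthy controls". For 2b, "Saliva samples will be collected from people with severe periodontitis and age and gender matched controls". Objective 1 has no such words; its aim is "To determine the underlying mechanism of regulation in monocytes/macrophages from people with periodontal disease compared with healthy controls".

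**Recruitment.** Under Sample size determination, Objective 1, "Approximately 150 gum disease (severe periodontitis) participants and 150 control participants (good gum health) will be approached", with 125 donors hoped for in each group. Controls are people attending regular dental appointments. Their disease criterion is "People with no evidence of periodontitis". Eligibility sets a lower age limit and no upper one. The recruitment, eligibility, sample-collection and sample-size sections give no matching procedure, ratio or age tolerance for any objective.

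**Saliva.** Under Sample Collection, Objective 1 and 2b, "The clinical practitioner will ask every 5th person to provide a saliva sample". The Objective 2a text does not repeat that rule: there, blood is taken "and saliva will be collected (2mls in total"). The Participants and recruitment section, however, states the one-in-five rule for everyone, without limiting it by objective.

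**Analysis.** "Data will be analysed by t-tests when two groups are compared", and ANOVA is used for more than two groups. No covariate is named.

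**The concern.** By promising matching in Objective 2, the protocol treats age and gender as factors that a case-control comparison of these markers should control. It gives no reason for controlling them in the comparisons of 12 and 20 per group and not in the comparison of 125 per group.

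Cases and controls also reach the study by different routes. Cases attend for periodontal assessment and must have Stage III/IV, Grade C disease; controls are regular attenders. Nothing in the design makes their age or sex distributions alike. If they differ, and if monocyte behaviour or protein level varies with age or sex, an unadjusted test credits that variation to periodontitis. A larger sample does not remove such a bias; it makes the bias more likely to reach significance.

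For 2b the problem is narrower. A rule based on arrival order pays no attention to age or sex, so carrying it out as written need not yield the matched controls that the objective describes.

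**Working it through.** **1. The plan's own figure.** Objective 1 states 125 per group, 90% power, a 50% change and p<0.005. No SD is given, so 125 can be neither confirmed nor refuted. Solved backwards (two-sided, normal approximation):

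- detectable d = (2.807 + 1.282) × √(2/125) = 0.517 SD
- implied coefficient of variation = 0.50 / 0.517 = 0.967

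**2. Saliva count for 2b, if nested in Objective 1.**

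- asked: 150/5 = 30 per group, equal to the 30 per group to be approached for 2b
- donors: 125/5 = 25 per group, against a target of 20

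The number is feasible. Matching is what the rule leaves open.

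**3. Room for matching in 2b.** Simulation with assumed inputs: age SD 12 years, 50% female, 1:1 pairs of the same sex within 5 years. The table gives the chance of at least 20 pairs.

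| Pool | No age difference | Difference 0.5 SD | Difference 1 SD |
|---|---|---|---|
| 25 cases, 25 controls | 0.28 | 0.15 | 0.015 |
| 30 cases, 30 controls | 0.93 | 0.79 | 0.30 |
| 25 cases, any of 125 controls | 1.00 | 0.998 | 0.97 |

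If both groups are sampled one in five, there is little slack. If the cases are sampled and controls are then sought for them among all 125, matching is readily achieved.

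**4. Bias and false positives in Objective 1.** The documents give no age or sex data, so these inputs are assumptions: age SD 14 years, difference in mean age Δ, within-group age-outcome correlation r, and no true disease effect.

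- spurious d = r × Δ / 14
- noncentrality = d × √(n/2), with 2n − 2 degrees of freedom
- false-positive rate = probability that a noncentral t exceeds the two-sided critical value in either direction

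Central case: d = 0.3 × 10/14 = 0.214. Noncentrality = 0.214 × √62.5 = 1.69. The critical value at 0.005 with 248 degrees of freedom is 2.83.

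| Δ, r | Spurious d | n per group | Rate at p<0.005 | Rate at p<0.05 |
|---|---|---|---|---|
| 0 years, any r | 0 | 125 | 0.5% | 5% |
| 5 years, 0.2 | 0.07 | 125 | 1.3% | 9% |
| 10 years, 0.3 | 0.21 | 125 | 13% | 39% |
| 15 years, 0.4 | 0.43 | 125 | 71% | 92% |
| 10 years, 0.3 | 0.21 | 20 (as in 2b) | 1.6% | 10% |

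At the coefficient of variation implied in step 1, 0.214 SD is an apparent change of 0.214 × 0.967 = 21%, against the 50% that the study is sized to detect.

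**5. Which contrasts are exposed.** Every experiment in Table I (A to F) contains at least one periodontitis-versus-control contrast, and those are exposed. Contrasts of treated with untreated cells inside one disease group, such as control cells with and without IGFBP6 silencing, are not affected if the same donors supply both arms. The protocol does not say whether they do.

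**The case against.** The strongest reply is that nothing shows an actual imbalance. Confounding needs both a difference in age or sex between groups and a relation of the marker to age or sex, and the documents quantify neither. Both groups share exclusions for smoking and vaping, cardiovascular disease, diabetes, autoimmune disease, recent antibiotics and several drug classes, and both must have at least 18 teeth. This stands: the contrasts are open to confounding, not shown to be confounded. The exclusions do not, however, restrict sex, or age beyond the lower limit.

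A reader might infer that the one-in-five rule makes matching impossible throughout Objective 2. The documents do not support that. The sample-collection section confines the rule to Objectives 1 and 2b, and for 2b controls could still be matched when approached or chosen within the pool.

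A reader might also take 39% as the headline error rate. That figure uses 0.05, whereas the only threshold in the protocol is p<0.005, where the same inputs give 13%. Both figures assume one two-group test on all 125 per group. Table I has three-group experiments, and the protocol does not say that every donor enters each of them. If donors were divided across the six experiments (about 125/6 = 21 per group, an assumption), the central case falls to 1.6% at 0.005 and 10% at 0.05.

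Finally, covariates are often left to a statistical analysis plan, which is not at hand and could add them. That is fair for adjustment. It does not answer the recruitment half of the point, because an analysis plan cannot match controls after they have been enrolled, and the only tests the protocol names are unadjusted. The protocol withholds the linking code from the researchers and is silent on whether age and sex accompany the samples, so adjustment may not be possible unless this is arranged.

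**Conclusion.** The point holds in limited form and should be fixed. The protocol controls age and gender by design in Objective 2 but states no such control, by design or analysis, for Objective 1. For 2b it promises matching but describes a selection rule that does not by itself produce it. The periodontitis-versus-control contrasts are open to age and sex bias; within-disease-group cell contrasts are not, given common donors.

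The size depends wholly on assumed inputs. With 125 per group, the false-positive rate at p<0.005 runs from the nominal 0.5% with no imbalance, through 1.3% and 13%, to 71% at the extreme assumption. It is lower where fewer donors enter a comparison. The documents do not support saying that the disease effects are confounded, or that 2b cannot be matched.

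**What to change.** 1. **Objective 1.** State that controls are frequency-matched to cases on sex and age band, and give the bands.
2. **Objective 2b.** Apply the one-in-five count to the periodontitis group only. For each saliva case, ask the next eligible control of the same sex and age band for saliva. Also reconcile the general one-in-five wording in Participants and recruitment with Objective 2a, where every participant gives saliva.
3. **Data and analysis.** Release age (or age band) and sex with each coded sample, and include both as covariates in the periodontitis-versus-control comparisons. The linking code can stay with the clinical team.

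The cost is some protocol wording and two fields on the sample code sheet. The downside is small: some control strata will fill before others, so a few willing controls may be turned away while recruitment to the remaining strata continues.

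### Objective 2 controls are described as age and gender matched, but the only analysis rule makes no provision for the matching; adjusting for both factors is a cheap gain in precision

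*Protocol*

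**What the plan says.** In the protocol's Objectives and methods, item 2, blood and saliva for Objective 2a come from patients "both pre and post treatment and age and gender matched healthy controls". For Objective 2b, "Saliva samples will be collected from people with severe periodontitis and age and gender matched controls". IGFBP6 and seven Wnt proteins are to be measured and "the levels in patients and controls statistically compared".

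The Analysis section is one sentence for the whole study: "Data will be analysed by t-tests when two groups are compared or by ANOVA if more than two groups are assessed". The test is chosen by the number of groups alone. The section does not say whether a t-test is paired or independent, and it names no covariate.

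Sample size determination gives counts per group. Objective 2a plans "samples of blood and saliva from 12 severe periodontitis and 12 control participant", with ">90% power to detect a 30% change in protein expression". Objective 2b plans "saliva samples from 20 people with severe periodontitis and 20 control participants", with 80% power for a 20% change. Neither statement mentions matching or a within-pair correlation.

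Under Sample Collection, "the clinical practitioner will then anonymise all samples by allocating a code to the samples", and the researchers do not hold the link. The text does not say which participant details accompany the code.

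**The concern.** Matching makes the two groups alike on age and gender. If either factor influences a protein, its contribution largely cancels from the patient-control difference. An independent-groups standard error still counts it as noise. The interval is then wider than it need be, and the p-value larger.

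The protocol takes on the recruitment burden of matching in its two smallest samples, 12 against 12 and 20 against 20. Its only analysis sentence does not carry the matching through. What is at stake is efficiency: a real biomarker difference could be missed that an adjusted analysis of the same samples would find.

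The point covers only the patient-control contrasts in Objective 2. It does not concern Objective 1, which is not described as matched. Nor does it concern the pre- and post-treatment samples from the same patient, which raise a separate question.

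**Working it through.** **Inputs from the protocol.** n = 12 per group with power above 90% (2a, taken as 90%); n = 20 per group with 80% power (2b); significance level 0.005.

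**Assumptions.** The tests are two-sided. Matching is close, and age and gender carry all of the matching correlation, so that rho is the share of protein variance they explain. rho is not in the protocol and is varied from 0 to 0.3, with 0.5 as an extreme.

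**The plan's own figures.** The sample sizes cannot be reproduced, because no standard deviation is given for the 30% or 20% change. The standardised difference d was therefore solved so that an independent t-test with 2n-2 degrees of freedom has exactly the stated power at 0.005:
- 2a: d = 1.837, noncentrality d·sqrt(n/2) = 1.837 × sqrt(6) = 4.50.
- 2b: d = 1.217, noncentrality 1.217 × sqrt(10) = 3.85.

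**Standard error.** With common variance s², the variance of the matched difference in means is 2s²(1-rho)/n. The independent-groups formula uses 2s²/n. The ratio of standard errors is 1/sqrt(1-rho): 1.05 at rho 0.1, 1.12 at 0.2, 1.20 at 0.3 and 1.41 at 0.5.

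**Power.** The independent t-test was simulated on 400,000 matched data sets per setting. The adjusted model uses the noncentral t with noncentrality d·sqrt(n/2)/sqrt(1-rho) and 2n-4 degrees of freedom. For 2b at rho 0.2, that is 3.85 × 1.118 = 4.30 on 36 degrees of freedom, giving 89.6%.

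| rho | 2a independent | 2a adjusted | Gain | 2b independent | 2b adjusted | Gain |
|---|---|---|---|---|---|---|
| 0 | 90.0% | 89.3% | -0.7 | 80.0% | 79.7% | -0.3 |
| 0.1 | 90.9% | 92.7% | 1.8 | 81.2% | 84.8% | 3.6 |
| 0.2 | 91.9% | 95.7% | 3.8 | 82.3% | 89.6% | 7.3 |
| 0.3 | 92.8% | 97.8% | 5.0 | 83.6% | 93.8% | 10.2 |
| 0.5 | 94.6% | 99.8% | 5.2 | 86.7% | 99.0% | 12.3 |

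**False-positive rate.** For the independent test in 2b it falls from the nominal 0.005 to about 0.0034, 0.002 and 0.0012 at rho 0.1, 0.2 and 0.3.

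**Other checks.**
- At two-sided 0.05 the pattern in 2b is similar: 82.5% against 87.8% at rho 0.2.
- Simulating 2b with an actual regression on age and gender, with control age only within 5 years of the patient's (assumed), gave 82.5% against 89.8% at rho 0.2.
- A strictly paired t-test is a poorer remedy. At rho 0 it drops power from 90.0% to 80.9% in 2a and from 80.0% to 73.9% in 2b, because it halves the degrees of freedom.

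**The case against.** **The rule does not exclude a matched analysis.** A t-test may be paired and an ANOVA may be blocked, and such detail is often left to an analysis plan, which is not at hand here. A reader might infer that the protocol commits to ignoring the matching. The text does not support that. What stands is that the rule it does state makes no provision for the matching, and that a better method can be named.

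**No planned power is lost.** In the table the independent test meets the stated power at every rho. A reader might infer that Objective 2 is underpowered or that its inference is invalid. Neither follows. The loss is measured against an attainable analysis. The error is conservative: false positives are not inflated, and ignoring the matching does not itself bias the difference.

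**rho is unknown.** A value of 0.5 would mean that age and gender explain half the protein variance, and nothing in the protocol supports that. The 12-point gain in 2b should not be taken as the expected size.

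**The matching itself is loosely described.** No ratio, age tolerance or pairing is given, and the sections on recruitment, eligibility and sample size do not mention matching. The Sample Collection text that covers 2b asks one participant in five for saliva, which is not a matched selection. If matching is loose, 1/sqrt(1-rho) is an upper limit. This objection stands. It favours covariate adjustment, which needs no pairs, over a paired test.

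**Coded samples.** A reader might infer that age and gender will be unavailable to the analysts. The protocol is silent on this. It is equally silent on whether patient or control status travels with the code, and that must happen for any comparison. This is a practical step to confirm and not a defect shown by the text.

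**Conclusion.** The point holds as a cheap improvement. Objective 2 describes matched controls, and the protocol's only analysis rule does not provide for the matching. If the comparison is run as an independent-groups test, and if age or gender influences the protein, then the standard error is overstated by up to 1/sqrt(1-rho) and attainable power is forgone.

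Over rho 0.1 to 0.3 the amount forgone is about 4 to 10 points in 2b and 2 to 5 points in 2a, and it disappears as rho approaches 0. These figures rest on an assumed rho, close matching, a two-sided 0.005 level, and effect sizes solved back from the stated power. The stated 80% and 90% are still met under those assumptions.

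**What to change.** In Analysis, state that the patient-control comparisons in Objective 2a (baseline samples) and Objective 2b will use a linear model of protein level on group, age and gender, reporting the adjusted group difference with its confidence interval. In Sample Collection, state that age (in years or a band) and gender are passed to the researchers with each sample code. It would also help to say how the matching is done and how it fits with asking only some participants for saliva.

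The model works whether matching is individual or by frequency, so it does not depend on that choice. The cost is one sentence in Analysis and two data items that the clinical team already needs for matching. Statistically it uses two degrees of freedom. If age and gender are unrelated to the protein, power falls from 90.0% to 89.3% in 2a and from 80.0% to 79.7% in 2b.

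### The analysis rule picks the test by the number of groups alone and ignores that Objective 2a measures the same patients twice beside a separate control group

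*Protocol*

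**What the plan says.** The whole of the Protocol's Analysis section is one sentence: "Data will be analysed by t-tests when two groups are compared or by ANOVA if more than two groups are assessed". It mentions neither pairing nor donors.

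Under Objectives and methods, item 2a reads: "Peripheral blood and saliva will be collected from patients with periodontal disease both pre and post treatment and age and gender matched healthy controls". Sample Collection for Objective 2a confirms that the later blood and saliva come from the same person, once dental treatment is complete (typically about 24 weeks). The planned numbers are small: "From these approaches we hope to obtain samples of blood and saliva from 12 severe periodontitis and 12 control participant".

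Each Table I experiment (A to F) sets two conditions in one donor type beside one condition in the other. Experiment A has two control-cell conditions and one periodontitis condition, and asks "Does silencing BP6 in control cells mimic efforts observed in cells from periodontal patients". Experiment C has two periodontitis conditions and one control condition, and asks "Does addition of IGFBP6 to cells from periodontal patients mimic control cells". The table does not say whether the two like-type conditions use cells from the same donors.

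On coding, Sample Collection says: "Only the clinical practitioners will have access to the code that links the samples and people, not the researchers". The text does not say whether one person's two samples carry a common code.

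**The concern.** Objective 2a yields three sets of values: patients before treatment, the same patients after it, and controls. Counting groups sends these to ANOVA. A one-way ANOVA treats all three sets as independent, which the first two are not. A purely repeated-measures ANOVA has no place for controls who are different people. Pairwise t-tests raise the same question for before versus after, because the rule does not say whether the test is paired.

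Two different errors are possible. If the link between a patient's two values is ignored, the before-after contrast is judged against an error term that still holds the differences between people, so it is conservative. If a patient's two values are counted as two independent people in a comparison with controls, that comparison is too liberal. Table I carries the same risk wherever one donor's cells are split between conditions. A paired analysis also needs the laboratory researchers to know which two samples belong together.

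**Working it through.** **Inputs.** From the Protocol, Sample size determination: 12 patients and 12 controls, a 30% change, power above 90%, and a significance level of 0.005 (taken as two-sided). The Protocol gives no SD and no correlation ρ between a person's two values. I assume ρ = 0.3, 0.5 and 0.7, Normal values and the same SD σ in all three sets.

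**1. The plan's own figure.** It cannot be reproduced without an SD, but it can be solved backwards.
- Normal approximation: d = (2.807 + 1.282) × √(2/12) = 1.669, so SD = 30/1.669 = 18%.
- Noncentral t with 22 degrees of freedom: d = 1.837, so SD = 30/1.837 = 16%.

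**2. Standard error of before versus after.** An independent-groups test uses √(2σ²/n). The true value is √(2σ²(1−ρ)/n). The overstatement is 1/√(1−ρ): 1/√0.7 = 1.20, 1/√0.5 = 1.41, 1/√0.3 = 1.83.

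**3. Controls versus both patient samples pooled as 24 independent values.** The assumed variance is σ²/24 + σ²/12 = 3σ²/24. The true variance is (1+ρ)σ²/24 + 2σ²/24 = (3+ρ)σ²/24. The standard error is understated by √((3+ρ)/3): 1.05, 1.08 and 1.11.

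**4. Rejection rates when nothing differs** (simulation, 100,000 runs, n = 12 per group, nominal 5%):

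| Test | ρ=0 | ρ=0.3 | ρ=0.5 | ρ=0.7 |
|---|---|---|---|---|
| Before v after, unpaired t | 5.0% | 2.2% | 0.9% | 0.2% |
| Before v after, three-group pooled error | 5.1% | 2.1% | 0.7% | 0.1% |
| Before v after, paired t | 5.0% | 5.0% | 5.0% | 5.0% |
| One-way ANOVA, overall test | 5.0% | 3.9% | 3.5% | 3.5% |
| Controls v pooled patient values | 5.1% | 6.2% | 7.1% | 8.2% |

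At nominal 0.5%, the unpaired t rejects 0.11%, 0.03% and under 0.01% of the time at ρ = 0.3, 0.5 and 0.7. Controls versus pooled patient values rejects 0.8%, 1.0% and 1.3%.

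**5. Power of before versus after at level 0.005**, n = 12:

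| Effect | Test | ρ=0.3 | ρ=0.5 | ρ=0.7 |
|---|---|---|---|---|
| d = 1.837 (implied by the 90% claim) | unpaired t | 93% | 95% | 96% |
| | paired t | 94% | 99% | >99% |
| d = 1.258 (50% power if independent) | unpaired t | 50% | 51% | 51% |
| | paired t | 59% | 78% | 96% |

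The second effect corresponds to a 30% change with an SD of 30/1.258 = 24% instead of 16%. At ρ = 0 the unpaired test is correct, and pairing would cost power (81% against 90% at d = 1.837).

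**The case against.** The sentence names families of tests, not their form. A paired t-test is a t-test, and ANOVA does not exclude a version with donor as a blocking factor. The exact form is often left to a statistical analysis plan, which is not at hand. A reader might infer that the rule has no valid reading and that the error bars are wrong. The Protocol does not support that: the errors arise only if independent-groups versions are used and ρ is not zero.

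A reader might also take it as fact that every Table I experiment splits one donor's cells. That is the natural reading of a vehicle or control reagent set against a treatment, but it is nowhere stated, and separate donors are possible.

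The comparison that item 2 names is patients against controls, and the mimicry questions in Table I also need contrasts between donors. The loss of precision in step 2 does not apply to those contrasts.

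Finally, withholding the identity key does not prevent a shared sample code. The clinical team keeps the key, and the three flow charts, which cannot be seen here, may describe labelling.

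These points stand and limit the finding. They do not remove it. The Protocol does state a selection rule, its only criterion is the number of groups, and Objective 2a plainly contains repeated measurements on the same people.

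**Conclusion.** The rule needs correcting for Objective 2a, and for Table I wherever donors are shared. Used with independent-groups tests, it overstates the standard error of the within-person contrast by 1.2 to 1.8 times for ρ from 0.3 to 0.7, and a nominal 5% test of that contrast has a true rate of about 2% down to 0.1-0.2%. Pooling a patient's two values against controls fails in the opposite direction, at 6.2% to 8.2%.

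A reader might conclude that real treatment effects will be missed. At the effect implied by the Protocol's own power claim they will mostly not be: the loss is about 1 to 4 percentage points. It becomes large only if the standardised effect is smaller than planned, for example 51% against 78% at d = 1.258 and ρ = 0.5. All values of ρ, and the back-solved SD, are assumptions. The structural point for Objective 2a does not depend on them.

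**What to change.** - For Objective 2a, and for Table I wherever one donor's cells are split between conditions, replace the sentence with a linear mixed model that has fixed group or condition effects and a random donor effect.
- Name the contrasts: after v before, or treated v untreated, within donor; periodontitis v control between donors, saying which patient sample is used.
- For before v after alone, specify a paired t-test. For patients v controls at one time point, specify a two-sample t-test.
- State for each Table I experiment whether the two like-type conditions share donors.
- Give each person's samples one study code plus a visit label, so that researchers can pair them without learning identity. This is best settled before samples are coded.

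The cost is Protocol wording and one labelling rule, with no extra participants or samples and no change to what researchers may know about identity.
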